1.2 Why is this study important?

Sleep Apnoea diagnosis currently takes place at a specialist clinic, primarily because the diagnostic devices are complicated to use and interpret, as well as expensive. The standard tests, which patients wear overnight, do not measure actual breathing but rely on a series of other measurements which indicate that the person has stopped or reduced their breathing.

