4.2 Current screening/diagnostic methods

Current screening and diagnostic devices for sleep apnoea are complicated, expensive and do not measure the breath pathway, they measure proxies for cessation of or reduction in respiration. They are also complicated and, even with the recent introductions of WatchPat™ and AcuPebble™, the median cost of current diagnostics is still in the region of £2-£3K per device plus consumables. This includes ResMed's NOX T3 diagnostic device illustrated above. Polysomnography (PSG) diagnostic devices can cost over £10,000 per unit depending on functionality. Some of the shortcomings with current 'home use' screening devices include, but are not limited to, the requirement for calibration, user error (complicated functionality), only nasal breath detection if respiration is monitored at all (most OSA patients breathe through their mouth), home damage and loss of device (not returned by patients).

ResMed's NOX T3

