6.3 Secondary Objectives

- To review whether the effectiveness of Apnea-Tech's Apne-Scan DC1 low-cost screener seems to be impacted by the severity of the user's condition determined by a standard sleep apnoea test device as:
 - Mild sleep apnoea
 - Moderate sleep apnoea
 - Severe sleep apnoea
- To review whether the effectiveness of Apnea-Tech's Apne-Scan DC1 low-cost screener seems to be impacted by the severity of the user's condition determined by a standard sleep apnoea test device as:
 - Mild hypopnoea
 - Moderate hypopnoea
 - Severe hypopnoea
- To review the participant's Apne-Scan data in comparison with their oxygen saturation levels from the standard test to identify the possibility of using the Apne-Scan data to predict the user's SPO2 level.
- To assess the usability and effectiveness of the device in capturing the minimum data required for screening for sleep apnoea.

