7.2 Outcome Measures

7.2.1 Research outcomes:

Primary Outcome

The primary outcome of interest is the data capture of the changing pressures in the user's breathing, whilst asleep, as recorded by the Apne-Scan DC1 device.

Note: The minimum evidence for successful completion of the study is 60 hours of breathing data captured by a minimum of 15 participants.

Secondary Outcomes

- An overall comparison of the OSA screening output from Apne-Scan DC1 with that from standard sleep apnoea test devices (ResMed NOX T3 and Phillips Alice Night One).
- A comparison stratified by the severity of the OSA indicated by standard sleep apnoea test devices.
- A comparison stratified by the severity of the hypopnoea indicated by standard sleep apnoea test devices.
- A possible first-generation algorithm, based on the Apne-Scan data, to predict the user's SPO2 level.

7.2.2 Safety Outcomes:

- Any adverse events (AEs) reported while performing the study procedures.
- Any adverse device effects (ADEs).

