10.3 Study Assessments

10.3.1. Schedule of Assessments

- Informed consent
- Demographic information (all standard care)
 - Age
 - Sex
 - Ethnicity
- Basic health criteria (all standard care)
 - Weight
 - Height
 - Neck circumference
 - Smoker/reformed smoker/non-smoker
 - Completes Epworth Sleepiness Questionnaire (validated)
 - Baseline Saturations at rest
- Issue of the Apne-Scan DC1 device, together with card documenting participants demographic information and basic health criteria
- Explanation to the participant of use of Apne-Scan at the same time as the standard sleep apnoea test device (either ResMed NOX T3 or Phillips Alice Night One)
- Participant uses the device overnight, at the same time as using the standard sleep apnoea test device.
- Participant completes short user questionnaire.
- Participant returns the Apne-Scan DC1 device and the completed participant questionnaire to the sleep clinic, at the same time as they return the standard sleep apnoea test device to the sleep clinic (standard care).
- Apnea-Tech analyses the data collected by Apne-Scan and provides to the clinical team.
- Output of Apne-Scan compared by clinical team to the output of the standard sleep apnoea test device used by the participant.

Schedule of study events					
Event	Enrolment	Baseline	Study	Analysis	Remarks
Clinical Data					
Informed Consent	X				
Age	X	X			
Sex		X			
Ethnicity		X			
Weight and height		X			
Neck circumference		X			
Smoking history		X			
Epworth Sleepiness questionnaire		X			
Baseline Saturations at rest		X			
Demonstration of use of Apne-Scan DC1		X			
Issue of Apne-Scan DC1 kit		X			

Apne-Scan Device					
Use of Apne-Scan DC1 overnight			X		

Post Apne-Scan Use					
Short participant experience questionnaire			X		
Return the device and questionnaire to the sleep clinic.			X		
Apne-Scan DC1 data is downloaded and secured together with clinical data and experience questionnaire, and participant's SPO2 data from the standard test for analysis				X	

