10.3.2.3 Device Usage and Data Flow

The Apne-Scan DC1 device is a single user, single use device. It has a single flow sensor which records the pressure in the breath pathway twice per second. The definitions for diagnosing sleep apnoeas and hypopneas are all relative, based on percentage changes in sensor readings. The device will only recognise Indicative Hypopnea Events, because it does not confirm desaturation, unless the captured data can be used to accurately predict the user's SPO2 level at any time. There is no need for any calibration by the clinician or the user.

Once the device has been started, it continues to monitor the pressure in the breath pathway until the battery runs flat, which is targeted at over eight hours. The pressure readings are recorded sequentially on the internal memory for later download. They remain in the memory when the battery has run down.

After use the study participant return the used Apne-Scan DC1 and completed questionnaire, with the standard test, to the sleep clinic. The Apne-Scan data, together with the post-use questionnaire and the standard test's SPO2 level data, will be securely stored by participant number by the company and then analysed for possible apnoeas, indicative hypopneas and prediction artifacts within the Apne-Scan data of changes in SPO2 levels.

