13. DATA ANALYSIS

13.1 Analysis of Endpoints

13.1.1 Summary Statistics

The summary statistics produced from this exploratory study will be:

% participants successfully using the Apne-Scan DC1

Comparisons of primary diagnostic metric, AHI, between the standard sleep apnoea test device and Apne-Scan (based on recorded apnoeas and indicative hypopneas).

Primary Data Analysis

Comparison of primary diagnostic metric, AHI, between the standard sleep apnoea test device and Apne-Scan DC1.

Secondary Data Analysis

Comparison of primary diagnostic metric, AHI, segmented into mild, moderate and severe sleep apnoea, between the standard sleep apnoea test device and Apne-Scan DC1

Comparison of primary diagnostic metric, AHI, segmented into mild, moderate and severe hypopnoea, between the standard sleep apnoea test device and Apne-Scan DC1

Comparison of the participant's Apne-Scan data with their oxygen saturation levels from the standard test to identify the possibility of using the Apne-Scan data to predict the user's SPO2 level, possibly resulting in a first-generation algorithm, based on the Apne-Scan data, to predict the user's SPO2 level.

Analysis of the usability and effectiveness of the device in capturing the minimum data required for screening for sleep apnoea.

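### Severity bands taken from the standard device's own AHI build regression to the mean into the severity comparison, tending towards apparent under-reading in severe disease

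*Combined protocol and SAP*

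**What the plan says.** Section 6.3 asks whether Apne-Scan's effectiveness seems to depend on the user's "condition determined by a standard sleep apnoea test device as" mild, moderate or severe, first for sleep apnoea and then for hypopnoea. Section 7.2 lists the matching outcome: "A comparison stratified by the severity of the OSA indicated by standard sleep apnoea test devices". Section 13.1.1 carries this out by comparing "AHI, segmented into mild, moderate and severe sleep apnoea, between the standard sleep apnoea test device and Apne-Scan DC1", with a parallel item for hypopnoea severity.

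The two recordings are made together on a single night (10.3.1: "Participant uses the device overnight, at the same time as using the standard sleep apnoea test device"). The protocol does not present the standard devices as error-free. Section 4.2 says that they "do not measure the breath pathway, they measure proxies for cessation of or reduction in respiration", and section 1.2 makes a similar remark. No error SD, repeatability figure, severity cut-off, agreement statistic or allowance for regression to the mean is given. Section 9 gives a sample size of 25 and describes the study as exploratory.

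**The concern.** Suppose two devices measure the same quantity with independent error, and people are grouped by one device's reading. Those in the top group are there partly because that device happened to read high. The other device does not share that error, so on average it reads lower in that group although neither device is biased. At the bottom of the scale the reverse happens.

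The planned stratification has this structure, so it pushes the answer to the 6.3 question in a known direction: apparent under-reading in severe disease. That direction also bears on the safety hypothesis in the Synopsis, which is that Apne-Scan does not miss moderate or severe disease. By section 1.8 the results feed the data analysis program, and by section 9 they feed the design of a powered study. The artefact is bias rather than imprecision, so a larger study using the same method would show it with more apparent certainty.

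**Working it through.** **Plan's own figure.** The sample size of 25 comes with no SD, effect, alpha or power, so there is nothing to reproduce.

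**Inputs from the documents.** Severity is set by the standard device (6.3, 7.2). The same AHI is compared within strata (13.1.1). Recording is simultaneous (10.3.1), so night-to-night variation is shared and only measurement and scoring error matters.

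**Assumptions, not in the documents.** Bands are cut at 5, 15 and 30 events/h. True AHI is lognormal with median 12 or 20 and log-SD s of 0.7 or 1.0. Both devices are unbiased, with independent multiplicative errors of log-SD e.

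**Step 1: expected slope.** With equal errors, the log difference (Apne-Scan minus standard) regressed on the log standard AHI has expected slope -e²/(s² + e²):
- e = 0.15: -0.0225/1.0225 = -0.02 (s = 1.0); -0.0225/0.5125 = -0.04 (s = 0.7)
- e = 0.25: -0.0625/1.0625 = -0.06; -0.0625/0.5525 = -0.11
- e = 0.35: -0.1225/1.1225 = -0.11; -0.1225/0.6125 = -0.20

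The slope is negative for any e above zero and is zero if the standard has no error.

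**Step 2: size in the severe band.** Simulation of 2,000,000 participants per scenario gives the mean difference in the severe band. A further 20,000 studies of n = 25 per scenario give the rate of a false 5%-level trend.

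| Error log-SD, both devices | Severe band by standard AHI, events/h | False trend on standard AHI | False trend on two-device mean |
|---|---|---|---|
| 0.15 | about -0.7 to -1.7 | 8-11% | 5% |
| 0.25 | about -2.0 to -4.3 | 13-21% | 5% |
| 0.35 | about -3.9 to -7.8 | 20-35% | 5% |

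The plan specifies no trend test, so the last two columns only illustrate how easily a trend could be misread.

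**Step 3: does the direction depend on the error model?** Twelve true-AHI distributions (lognormal, normal, exponential, and two mixtures with 25% or 40% non-apnoeic) were crossed with additive error of SD 3 or 6 events/h and proportional error of CV about 0.2 or 0.4. This makes 48 scenarios.
- Severe band: negative in 48 of 48, from -0.3 to -9.9 events/h.
- Mild band: positive in 32 of 48 (all 24 with proportional error, 8 of 24 with additive error), from -1.6 to +5.3.

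For additive normal error, E[A - S | S = s] = σ² × d/ds log f(s), where A is the Apne-Scan AHI, S the standard AHI, f the density of S and σ the error SD. The sign in a band therefore follows the slope of the density there. With 25% of participants below 5, the rest lognormal with median 20, and additive SD 6, the differences are +2.2 below 5, -0.4 mild, -1.5 moderate and -2.0 severe. The upward shift then falls below the mild band.

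**Step 4: does using the two-device mean cure it?** With equal errors, yes: all bands lie within about 0.1 events/h of zero. With unequal errors (e_A for Apne-Scan, e_S for the standard), the log-scale slope on the mean is [(e_A² - e_S²)/2] / [s² + (e_A² + e_S²)/4]. Take e_S = 0.15, e_A = 0.35 and s = 0.7:
- on the mean: 0.05/0.52625 = +0.10
- on the standard: -0.0225/0.5125 = -0.04

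Simulated at median 15 and n = 25, false trends are 7% on the standard and 14% on the mean. The severe-band difference is -1.4 events/h with standard bands and +3.2 with mean bands. The error-variance ratio here is 0.1225/0.0225 = 5.4. With an error-free standard and Apne-Scan error of about 40%, standard bands give about 0 and mean bands give +2.5 to +6.1 in severe.

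**The case against.** Several objections stand in whole or in part.

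- **Size.** Calling the reference a proxy measurement is the sponsor's rationale for its own device and is not an error estimate. Simultaneous recording removes night-to-night variation, so the artefact could be below 1 event/h. This stands, and the size can only be given conditionally.
- **Mild band.** A reader might infer that over-reading in mild disease is certain. The documents do not support that. Section 4.1 puts more than 25% of referrals as snorers, so mild is a middle band, and step 3 shows that it can go either way.
- **Remedy.** A reader might also infer that bands based on the mean of the two devices should replace the standard's bands. Step 4 rules this out as a sole analysis. Apne-Scan has one sensor sampled twice per second, and by 10.3.2.3 "The device will only recognise Indicative Hypopnea Events, because it does not confirm desaturation", so it may well be the noisier device. Mean-based bands could then hide true under-reading.
- **The question asked.** Sections 6.3 and 7.2 ask about severity as reported by the standard device, and that class is the natural one for classification tables. This stands, and is a reason to keep those bands.
- **Vagueness and scope.** Section 13.1.1 names no statistic or test, and a cross-tabulation would fit its wording. The analysis is secondary and exploratory, with about 1 to 13 participants expected in each of the mild, moderate and severe bands. This lowers the stakes. It does not remove the problem, because nothing in the plan warns against reading band-by-band AHI differences as a severity effect.

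**Conclusion.** The point holds in a limited form. Because the standard AHI is both the stratifier and half of the comparison, any error in it makes an unbiased Apne-Scan tend to appear to under-read in the severe band. The effect in the mild or lowest band is possible over-reading, with the location depending on the error model and on how many participants lie below mild. The severe-band artefact is roughly -1 to -8 events/h for assumed equal log-SD errors of 0.15 to 0.35, and nil if the standard is error-free. These figures rest on assumed AHI distributions, cut-offs and independent errors, none of which the documents supply.

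A reader might go further and treat any observed under-reading in severe disease as artefact. That does not follow. Apne-Scan is not known to be unbiased, since its hypopnoeas lack desaturation confirmation, and a real shift would be superimposed on the artefact. The supportable statement is that a trend across standard-device bands cannot by itself distinguish the two. This is an inexpensive improvement to a secondary analysis and does not undermine the study.

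**What to change.** In 13.1.1:

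1. Keep the standard-device severity bands for classification tables (for example, how many standard-device moderate or severe cases Apne-Scan places lower) and for descriptive summaries. State that a trend in the AHI difference across these bands is not by itself evidence of a severity effect.
2. Add a plot and regression of the paired log difference on the mean of the two devices' AHIs, with a stated rule for zero AHI values.
3. Add a Deming (errors-in-variables) analysis over a wide range of error-variance ratios, Apne-Scan to standard, for example from 0.5 to at least 6. A range of 0.5 to 2 would miss the 5.4 case above.
4. Report dependence on severity only if its direction holds across that range.
5. Do the same for the hypopnoea strata.
6. Do not use mean-based classes as the sole analysis.

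No new data are needed. The cost is a little more analysis and, with 25 participants, a less definite statement about severity.

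### The hypopnoea-severity analysis compares only total AHI, so it does not isolate Apne-Scan's error on hypopnoeas; separate apnoea and hypopnoea indices would do so

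*Combined protocol and SAP*

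**What the plan says.** Section 6.3 and the synopsis set two parallel secondary objectives. Each asks whether the effectiveness of the "low-cost screener seems to be impacted by the severity of the user's condition determined by a standard sleep apnoea test device as" mild, moderate or severe, first for sleep apnoea and then for hypopnoea. Section 7.2.1 and the synopsis give hypopnoea its own outcome, "A comparison stratified by the severity of the hypopnoea indicated by standard sleep apnoea test devices", without naming a metric.

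Section 13.1.1 supplies the metric. The hypopnoea analysis, which sets Apne-Scan against the reference device, is "Comparison of primary diagnostic metric, AHI, segmented into mild, moderate and severe hypopnoea". The sleep-apnoea analysis is "Comparison of primary diagnostic metric, AHI, segmented into mild, moderate and severe sleep apnoea", and the primary analysis uses AHI as well. The summary statistics describe the AHI comparison as "between the standard sleep apnoea test device and Apne-Scan (based on recorded apnoeas and indicative hypopneas" (the bracket closes there). AHI is missing from the abbreviation list, so this note is what shows that the Apne-Scan figure is a composite.

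No section plans a hypopnoea index, a separate hypopnoea count or event-level agreement, and none gives cut-points for the hypopnoea bands.

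On the device itself, Section 10.3.2.3 says: "The device will only recognise Indicative Hypopnea Events, because it does not confirm desaturation". It makes one exception, for the case where SPO2 turns out to be predictable from the Apne-Scan recording. Section 1.1 makes an oxygen fall of at least 3% part of what a hypopnoea is.

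**The concern.** Section 2 defines sleep apnoea to include hypopnoea, so the second objective adds something only if hypopnoea is treated on its own. The plan does this at most through the stratifier. The quantity compared inside each stratum is still apnoeas plus hypopnoeas.

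Hypopnoea is also where the two devices' definitions differ, because desaturation is part of the protocol's definition and Apne-Scan does not measure it. Pooling the two event types before comparing hides the source of any disagreement. Section 9 says the results will inform a powered study, and Section 1.8 says they will be used to develop the analysis program. Both uses need to know which event type produces the disagreement.

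**Working it through.** **Nothing to reproduce.** Section 9 gives 25 participants without alpha, power, effect size or SD. No event rates are given either, so every rate below is an assumption chosen to show how the metric behaves.

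**1. Identity.** With AI the apnoea index and HI the hypopnoea index, AHI = AI + HI, so for each participant

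AHI difference = AI difference + HI difference.

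One number cannot be split back into two.

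**2. Cancelling errors.** Assume reference AI = 10/h and HI = 20/h (AHI 30).

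| Apne-Scan AI + HI | AHI difference | HI error |
|---|---|---|
| 15 + 15 | 0 | -5/20 = -25% |
| 5 + 25 | 0 | +5/20 = +25% |
| 20 + 10 | 0 | -10/20 = -50% |
| 0 + 30 | 0 | +10/20 = +50% |

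Exact cancellation is what results when one event type is scored as the other.

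**3. Event mix.** Assume apnoeas are counted exactly and hypopnoeas over-counted by 40%, in two patients with reference AHI 30.

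- 28 apnoeas and 2 hypopnoeas per hour: 28 + 2 × 1.4 = 30.8 (+2.7%).
- 2 apnoeas and 28 hypopnoeas per hour: 2 + 28 × 1.4 = 41.2 (+37.3%).

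At 20% over-counting the results are 30.4 (+1.3%) and 35.6 (+18.7%). If the bands are cut on AHI, both patients fall in the same band. If they are cut on reference HI (2/h against 28/h), they very likely fall in different bands and the contrast shows.

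**4. AHI within hypopnoea strata.** In stratum s, with proportional errors eA and eH,

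mean AHI difference = eA × mean(AI in s) + eH × mean(HI in s).

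A simulation of 200,000 participants assumed independent gamma rates (AI shape 1, scale 10, mean 10/h; HI shape 1.5, scale 10, mean 15/h) and bands of reference HI at 5 to 15, 15 to 30, and 30 or more per hour:

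| Error pattern | Overall AHI difference | AHI difference by band | HI difference by band |
|---|---|---|---|
| HI +30% | 4.50 | 2.89, 6.33, 12.36 | 2.89, 6.33, 12.36 |
| AI +45% | 4.48 | 4.48, 4.48, 4.44 | 0, 0, 0 |
| AI -45%, HI +30% | 0.02 | -1.59, 1.85, 7.92 | 2.89, 6.33, 12.36 |

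The overall figures agree with direct arithmetic: 0.30 × 15 = 4.5, 0.45 × 10 = 4.5, and -4.5 + 4.5 = 0. Overall AHI therefore does not distinguish the first two patterns and misses the third. Within HI bands, the third pattern has the wrong level, and the wrong sign in the mild band. Its steps are nevertheless about right: 3.44 and 6.07 for AHI against 3.44 and 6.03 for HI. That depends on independence. If AI varies with HI, the eA term also changes across bands and contaminates the steps.

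**5. Precision of a direct HI comparison.** The 95% half-width for a mean paired difference is t(0.975, n-1)/√n, in units of the SD of the differences (not given in the documents).

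- n = 25: 0.41 SD. n = 15, the minimum in Section 7.2.1: 0.55 SD.
- Each limit of agreement: about 0.72 SD at n = 25 and 0.97 SD at n = 15.
- Three even bands: 25/3 ≈ 8 gives 0.84 SD; 15/3 = 5 gives 1.24 SD.

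**The case against.** The strongest reply is that the objective makes hypopnoea severity the stratifier and does not ask for agreement on hypopnoea counts. If AHI is the measure of effectiveness, comparing AHI within hypopnoea bands matches both the objective and the outcome. Step 4 supports this in part: with bands cut on reference HI and independent rates, the trend across severity is recovered almost exactly. This stands. A reader might infer that the hypopnoea objective goes unanswered, but the documents do not support that. What remains is that the level is biased by apnoea error, and the trend is safe only under an assumption about case mix.

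A reader might also infer from step 3 that the plan averages the two patients. That holds only if the bands are cut on AHI. Section 7.2.1 refers to hypopnoea severity as indicated by the reference device, which could well mean a hypopnoea rate; the plan does not say.

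Two further inferences fail. Nothing states that apnoea detection is the device's strength, since Section 5.2 reports that prototypes recognised both event types. And the lack of desaturation confirmation is conditional: Section 13.1.1 plans SPO2 work aimed at that gap, though only as an exploratory aim.

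It is also fair that this is one descriptive secondary analysis in an exploratory study, with no test or decision rule. Retained Apne-Scan data (seven years, Section 12.3) could be split by event type later. The same is not assured for the reference device, whose event counts are not among the data listed in Section 12.2.

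**Conclusion.** The point holds in a limited form. The hypopnoea-severity analysis rests on total AHI alone, which gives indirect information but does not isolate or attribute hypopnoea error. Under the assumed rates, an AHI difference of zero is compatible with hypopnoea errors from -50% to +50%, and a mean AHI difference of about 4.5/h can come wholly from either event type. If the undefined bands are cut on AHI, the second analysis also duplicates the first. These sizes illustrate how the metric behaves and do not predict Apne-Scan's performance. The textual finding needs no assumption beyond the note in Section 13.1.1 on what AHI contains. The primary analysis can stay as it is, and neither deleting the hypopnoea strata nor rewording the objective is needed.

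**What to change.** In Section 13.1.1, keep the AHI comparisons and add for each participant:

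- the paired difference in apnoea index, Apne-Scan minus reference;
- the paired difference between Apne-Scan's indicative hypopnoea index and the reference hypopnoea index.

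Report both descriptively, overall and by hypopnoea stratum. State in advance that the hypopnoea strata are cut on the reference hypopnoea index, not on AHI, and give the cut-points.

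**Cost.** On the Apne-Scan side there is no new measurement, because Section 10.3.2.3 already has the data analysed for apnoeas and indicative hypopnoeas. On the reference side, the clinical team, which makes the comparison under Section 10.3.1, must record event counts by type. Section 12.2 does not list these, and Section 1.6 has the company receive only oxygen saturation from the standard test, so the data-collection text needs an addition as well. Results by stratum will be imprecise, with about 5 to 8 participants each if the split is even, and fewer if some have no sleep apnoea. They should be presented as descriptive.
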